6.2. Subject Withdrawal

Subjects may withdraw from the study at any time at their own request, or they may be withdrawn at any time at the discretion of the investigator or sponsor for safety, behavioral, or administrative reasons. If a subject does not return for a scheduled visit, every effort should be made to contact the subject. In any circumstance, every effort should be made to document subject outcome and pregnancy outcome, if possible. The investigator should inquire about the reason for withdrawal, request the subject to return all unused investigational product(s), request the subject to return for a final visit, if applicable, and follow-up with the subject regarding any unresolved adverse events.

If the subject withdraws from the study and also withdraws consent for disclosure of future information, no further evaluations should be performed and no additional data should be collected. The sponsor may retain and continue to use any data collected before such withdrawal of consent.

Unless a subject withdraws the consent or leaves the town/village, she should continue in the study for follow up visits through Day 42, and following delivery or termination of pregnancy for EIU safety assessment. Subject may be withdrawn from the study treatment (during the first three days) due to safety concerns (eg, adverse events, significant laboratory abnormalities, and contraindications of concomitant medications), but not from the clinical study per se unless the subject withdraws consent. The standard antenatal care including IPTp will be given to the subject per local ANC guideline. The circumstances and data surrounding these events should be clearly documented in the case report form. The

investigator must determine the primary reason for discontinuation. A discontinuation must be reported immediately to the Pfizer medical monitor or his/her designated representative if it is due to a serious adverse event (SAE).

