9.2.1. Analysis of Primary Endpoint

The proportion of subjects with parasitological response (PCR corrected) at Day 28 post first dose of study medication will be estimated for the primary endpoint using the MITT and PP subject populations. The proportion will be estimated from the Kaplan-Meier curve based on the time to the first occurrence of parasitological failure (PCR corrected). Use of the Kaplan-Meier curve/product limit estimator is recommended by WHO⁸ and has been used in analyzing primary efficacy endpoints in late stage antimalarial treatment clinical trials.⁹²⁻⁹⁴

A subject will be a parasitological responder if she has a zero parasite count on the Day 7 visit without subsequent recrudescence (PCR corrected) through the day of consideration, otherwise she is a parasitological failure. In addition, subjects who withdraw from the study treatment during the first three days due to development of malaria symptoms and are administered antimalarial standard of care treatment for malaria in pregnancy, will be considered parasitological failures. The time (number of days) to the first occurrence of parasitological failure will be the analysis variable. The time in days is defined as [date of the parasitological failure event – date of the first dose of study medication + 1].

Subjects who do not experience the defined event (parasitological failure) will be censored as follows:

- Subjects who withdraw from the study early due to any reason will be censored on the day of the last available blood smear measurement;
- Subjects who continue on in the study but have all remaining blood smears missing from a given point in time onward will be censored on the day of the last available smear;
- Subjects completing the Day 42 visit post first dose of study medication will be censored on the day of the last available blood smear measurement;
- Subjects receiving any concomitant antimalarial for reinfection (PCR corrected) or in the absence of parasitemia will be censored at the visit date if the antimalarial is given after collection of the blood smear on that day. Otherwise the subject will be censored on the day of the last available previous blood smear measurement;
- Subjects who are lost to follow-up without any follow-up blood smears will have a censored duration of 1 day.

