The proportion of subjects with parasitological response (PCR corrected) at Day 28 (primary) will be estimated from the Kaplan-Meier curve and its standard error estimated by the Greenwood formula. If less than 100%, a two-sided 95% confidence interval for the estimated proportion of subjects with parasitological response will be computed.

Additional sensitivity analyses will also be performed using the MITT and PP subject populations. The sensitivity analyses will consider premature discontinuation due to any reason as parasitological failure, if not already a parasitological failure due to a defined event. The same statistical methods will again be used to estimate the proportion of subjects with parasitological response (PCR corrected) at Day 28.

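### The sensitivity analysis fails only women recorded as discontinued, so women who stay in the study without smears remain censored, and the imputed failure has no date

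*Protocol*

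**What the plan says.** Protocol section 9.2.1 estimates the Day 28 response from a Kaplan-Meier curve of time to first parasitological failure. Its censoring list treats three kinds of missing follow-up separately:

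- Early withdrawal: "Subjects who withdraw from the study early due to any reason will be censored on the day of the last available blood smear measurement".
- Staying in the study without smears: "Subjects who continue on in the study but have all remaining blood smears missing from a given point in time onward will be censored". The censoring time is that of her final smear.
- Loss with no follow-up smear at all: "Subjects who are lost to follow-up without any follow-up blood smears will have a censored duration of 1 day".

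The sensitivity analysis, in the MITT and PP populations, then changes one thing: "The sensitivity analyses will consider premature discontinuation due to any reason as parasitological failure", unless the woman has already failed. Otherwise "The same statistical methods will again be used to estimate the proportion of subjects" with response at Day 28. Section 9.2.2 carries these sensitivity analyses over to the secondary response endpoints.

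The only definition of failure time in 9.2.1 counts from the first dose to the "date of the parasitological failure event", plus one day. No date is given for a failure that is imputed because of discontinuation.

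On retention, section 6.2 says: "Unless a subject withdraws the consent or leaves the town/village, she should continue in the study for follow up visits through Day 42". Safety follow-up then runs on until after delivery or termination. The same section states that a woman taken off study treatment is not thereby taken out of the study.

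**The concern.** A sensitivity analysis of this kind should show what happens to the Day 28 rate if women whose outcome is unknown are treated as failures. The trigger chosen is an administrative status, discontinuation, rather than the missing outcome. The protocol itself recognises women who have not discontinued and yet have no further smears.

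That group can arise in practice. Section 4.1 admits women at 14 to 30 weeks of gestation, so on Day 28 a woman is at most at about 34 weeks. Follow-up then continues until after delivery, and section 6.1.6 lets fieldworkers complete that last visit at home. A woman who misses every smear visit after Day 7 but is seen after delivery has not left the study. She has no Day 28 outcome, and she is censored in both the primary and the sensitivity analysis.

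This is the only check on loss that the protocol states for the primary endpoint. If part of the loss escapes it, a small shift from the primary estimate could be read as robustness when it partly reflects how loss was recorded.

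**Working it through.** The protocol gives no numerical result for the sensitivity analysis, so there is none to reproduce. The check asks how far the Day 28 estimate moves as more or fewer of the women without an outcome are counted as failures.

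**Inputs**
- 166 women and about 10% dropout (section 9.1): 166 × 0.10 = 16.6, taken as 17 women, leaving 149.
- 8 observed failures by Day 28. This is an assumption, in line with the 95% planning incidence in section 9.1 (0.05 × 166 = 8.3).
- When the 17 are lost, and how many are recorded as discontinued. The protocol gives neither, so both are varied.

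**Simple case: all 17 lost before the first observed failure**
- All 17 censored, as in the primary analysis: 1 − 8/149 = 94.6%.
- 5 recorded as discontinued and failed by Day 28, 12 still censored: (154 − 8 − 5)/154 = 141/154 = 91.6%.
- All 17 failed by Day 28: (166 − 8 − 17)/166 = 141/166 = 84.9%.

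**Losses spread over the visits** (an assumed pattern: last information on Day 1 for 5 women, and on Days 7, 14 and 21 for 4 each; observed failures 2, 3 and 3 on Days 14, 21 and 28)
- Numbers at risk: 166 − 5 − 4 = 157 on Day 14; 157 − 2 − 4 = 151 on Day 21; 151 − 3 − 4 = 144 on Day 28.
- All 17 censored: (155/157) × (148/151) × (141/144) = 94.7%, 95% half-width 3.5 points by Greenwood.

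With the imputed failures placed at the last-information day, the estimate by share of the 17 counted as failures by Day 28 is:

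| Share counted | Day 28 estimate |
|---|---|
| 0% | 94.7% |
| 25% | 92.2% |
| 50% | 89.7% |
| 75% | 87.3% |
| 100% | 84.9% (half-width 5.4 points) |

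The timing of the losses hardly matters. The share counted decides the result, over a range of nearly 10 points.

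**Date of the imputed failure.** Take a woman last smeared on Day 14 and declared withdrawn on Day 35.
- Dated at her last smear, she fails on Day 14 and counts as a Day 28 failure.
- Dated at the first missed visit, she fails on Day 21 and counts.
- Dated at the discontinuation, she is event-free through Day 28 and does not count.

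Section 9.2.1 does not say which applies. The choice matters only for women whose last smear precedes Day 28. A woman with a clear Day 28 smear who withdraws later is correctly a Day 28 responder under any of the three.

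**The case against.** The best defence is that the trigger is broad. It covers discontinuation for any reason, and women who leave the area or cannot be traced would ordinarily be recorded that way. Section 6.2 is a retention instruction and does not define who is recorded as discontinued. The synopsis and section 9 time the early analysis by each woman either reaching Day 42 or withdrawing early, which suggests that few would be neither. Section 9 leaves detailed methods to an Analysis Plan, where an imputation date could be fixed. The study is supportive, with one arm and no hypothesis test, so no decision threshold depends on this analysis.

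Much of this stands. The documents give no basis for the size of the group that stays in the study without smears, nor for saying that most non-attenders would belong to it. But 9.2.1 lists the group as distinct from early withdrawal, and the sensitivity rule leaves it out. That is a stated rule that is too narrow, not a detail left for later.

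A reader might go further and infer that failures are dated by the discontinuation, so that the check is nearly empty. If all 17 women were lost early and all were declared withdrawn after Day 28, that reading would give (166 − 8)/166 = 95.2%, above the primary estimate. The documents do not support this as a description of the plan. The time formula was written for observed events, and the instruction to reuse the same methods is equally compatible with failing a woman at the day on which she would have been censored. Nor is the check empty in general: if the expected dropouts are recorded and dated by Day 28, it lowers the estimate by nearly 10 points.

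**Conclusion.** The concern holds in a limited form. As written, the sensitivity analysis omits women who remain in the study with all remaining smears missing, so its strength depends partly on whether loss is recorded as discontinuation. Under the protocol's 10% dropout and an assumed 8 failures, the Day 28 estimate can fall anywhere between about 94.6% and 84.9%. The 5-to-12 split that gives 91.6% is an illustration, not a forecast. The date of the imputed failure is open; it is not shown to be wrong. The primary estimate is unaffected, and the correction is worth making because it is cheap and this is the only stated check on loss.

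**What to change.** In section 9.2.1, replace the discontinuation trigger with the missing outcome:

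- **Who fails:** any woman who is not already a failure, is not censored under the concomitant-antimalarial rule, and has no blood smear at or after the Day 28 visit, whether or not she formally left the study.
- **When:** at the first scheduled smear visit missed after her last available smear. For these women that is the Day 28 visit at the latest. Under the section's time formula an on-schedule Day 28 visit has time 28 + 1 = 29, so the Kaplan-Meier estimate must be read to include that visit.
- **Secondary endpoints:** the same rule at each of the other visit days, with the matching antimalarial rule from section 9.2.2 for the PCR-uncorrected analyses.

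The cost is one paragraph of text and no new data. The sensitivity estimate will be less favourable where women stay in the study without smears. The primary analysis does not change.

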9.2.2. Analysis of Secondary Endpoints

The secondary parasitological response endpoints will be analyzed in the same manner as the primary endpoint, and will use the ITT, MITT, and PP subject populations. These analyses will be done using both PCR corrected and uncorrected results, and will also include the sensitivity analyses.

For PCR corrected, censoring will be done in the same manner as for the primary endpoint. For PCR uncorrected, censoring will be as follows for subjects who do not experience parasitological failure:

- Subjects who withdraw from the study early due to any reason will be censored on the day of the last available blood smear measurement;
- Subjects who continue on in the study but have all remaining blood smears missing from a given point in time onward will be censored on the day of the last available smear;
- Subjects completing the Day 42 visit post first dose of study medication will be censored on the day of the last available blood smear measurement;
- Subjects receiving any concomitant antimalarial in the absence of parasitemia will be censored at the visit date if the antimalarial is given after collection of the blood smear on that day. Otherwise the subject will be censored on the day of the last available previous blood smear measurement;
- Subjects who are lost to follow-up without any follow-up blood smears will have a censored duration of 1 day.

For parasite counts, descriptive statistics (N, mean, SD, standard error, median, minimum and maximum) will be provided at each time point on actual counts.

9.3. Safety Analysis

Adverse events, history of concomitant treatments, hemoglobin, temperature, and the EIU safety assessment will be recorded for each subject during the study according to the schedule of assessments. Standard safety reporting tables will summarize and list the safety data.

Each adverse event will be counted once according to the date of onset. If the adverse event onset was prior to the first dose of study drug and the event does not increase in severity after initiation of study drug, the adverse event is then considered to be a pre-treatment adverse event and will not be counted in the treatment-emergent adverse event incidence tables. If the onset is prior to the first dose of study drug and the severity increases thereafter, the event is counted as a treatment-emergent adverse event. An adverse event with onset after the first dose of study drug will be counted as a treatment-emergent adverse event. This rule is consistent with the treatment-emergent signs and symptoms (TESS) convention for counting adverse events.

9.4. Pharmacokinetic Analysis

The PK concentration population is defined as all subjects who have received at least 1 dose and have at least 1 blood sample collected for PK analysis prior to subject withdraw from the study, if applicable.

Individual concentrations of AZ, CQ, and desethyl-CQ will be summarized via descriptive statistics by nominal time and listed by nominal time and actual time. Actual PK sampling times will be used in the derivation of PK parameters. As data permitting, all PK concentration data may contribute to characterizing the PK of AZCQ using a population PK approach with pooled data from other studies and will be reported separately. Actual PK sampling times will be used in the derivation of PK parameters.

9.5. Interim Analysis

None.

9.6. Independent Data Monitoring Committee (IDMC)

An IDMC external from Pfizer will oversee the study for safety aspects, and will review emerging safety data on an ongoing basis. The full composition of the IDMC and the guidelines for oversight of this study will be specified in the IDMC charter.

10. QUALITY CONTROL AND QUALITY ASSURANCE

During study conduct, Pfizer or its agent will conduct periodic monitoring visits to ensure that the protocol and GCPs are being followed. The monitors may review source documents to confirm that the data recorded on CRFs is accurate. The investigator and institution will allow Pfizer monitors or its agents and appropriate regulatory authorities direct access to source documents to perform this verification.

The study site may be subject to review by the Institutional Review Board (IRB)/Independent Ethics Committee (IEC), and/or to quality assurance audits performed by Pfizer, or companies working with or on behalf of Pfizer, and/or to inspection by appropriate regulatory authorities.

090177e1811d3ccb\Approved\Approved On: 19-Feb-2010 20:59

It is important that the investigator(s) and their relevant personnel are available during the monitoring visits and possible audits or inspections and that sufficient time is devoted to the process.

11. DATA HANDLING AND RECORD KEEPING

11.1. Case Report Forms/Electronic Data Record

As used in this protocol, the term Case Report Form (CRF) should be understood to refer to either a paper form or an electronic data record or both, depending on the data collection method used in this study.

A CRF is required and should be completed for each included subject. The completed original CRFs are the sole property of Pfizer and should not be made available in any form to third parties, except for authorized representatives of Pfizer or appropriate regulatory authorities, without written permission from Pfizer.

The investigator has ultimate responsibility for the collection and reporting of all clinical, safety and laboratory data entered on the CRFs and any other data collection forms (source documents) and ensuring that they are accurate, authentic / original, attributable, complete, consistent, legible, timely (contemporaneous), enduring and available when required. The CRFs must be signed by the investigator or by an authorized staff member to attest that the data contained on the CRFs is true. Any corrections to entries made in the CRFs, source documents must be dated, initialed and explained (if necessary) and should not obscure the original entry.

In most cases, the source documents are the hospital's or the physician's subject chart. In these cases data collected on the CRFs must match the data in those charts.

In some cases, the CRF, or part of the CRF, may also serve as source documents. In these cases, a document should be available at the investigator's site as well as at Pfizer and clearly identify those data that will be recorded in the CRF, and for which the CRF will stand as the source document.

11.2. Record Retention

To enable evaluations and/or audits from regulatory authorities or Pfizer, the investigator agrees to keep records, including the identity of all participating subjects (sufficient information to link records, eg, CRFs and hospital records), all original signed informed consent forms, copies of all CRFs, serious adverse event forms, source documents, and detailed records of treatment disposition, and adequate documentation of relevant correspondence (eg, letters, meeting minutes, telephone calls reports). The records should be retained by the investigator according to ICH, local regulations, or as specified in the Clinical Study Agreement, whichever is longer.

090177e1811d3ccb\Approved\Approved On: 19-Feb-2010 20:59

If the investigator becomes unable for any reason to continue to retain study records for the required period (eg, retirement, relocation), Pfizer should be prospectively notified. The study records must be transferred to a designee acceptable to Pfizer, such as another investigator, another institution, or to an independent third party arranged by Pfizer. The investigator must obtain Pfizer's written permission before disposing of any records, even if retention requirements have been met.

12. ETHICS

12.1. Institutional Review Board (IRB)/Independent Ethics Committee (IEC)

The IRB/IEC of London School of Hygiene and Tropical Medicine (LSHTM) is planned to be used in this study in addition to local IRB/IEC. Study related documentation will be reviewed by the LSHTM IRB/IEC and the local IRB/IEC. No subjects will be enrolled in the study until the approvals from both LSHTM IRB/IEC and local IRB/IEC are received. It is the responsibility of the investigator to have prospective approval of the study protocol, protocol amendments, informed consent forms, and other relevant documents, eg, recruitment advertisements, if applicable, from the IRB/IEC. All correspondence with the IRB/IEC should be retained in the Investigator File. Copies of IRB/IEC approvals should be forwarded to Pfizer.

The only circumstance in which an amendment may be initiated prior to IRB/IEC approval is where the change is necessary to eliminate apparent immediate hazards to the subjects. In that event, the investigator must notify the IRB/IEC and Pfizer in writing immediately after the implementation.

12.2. Ethical Conduct of the Study

The study will be conducted in accordance with the Declaration of Helsinki on Ethical Principles for Medical Research Involving Human Subjects, adopted by the General Assembly of the World Medical Association (1996).

In addition, the study will be conducted in accordance with the protocol, the International Conference on Harmonization guideline on Good Clinical Practice, and applicable local regulatory requirements and laws.

12.3. Subject Information and Consent

All parties will ensure protection of subject personal data and will not include subject names on any sponsor forms, reports, publications, or in any other disclosures, except where required by laws. In case of data transfer, Pfizer will maintain high standards of confidentiality and protection of subject personal data.

The informed consent and assent form must be in compliance with ICH GCP, local regulatory requirements, and legal requirements. Assent will be obtained from subjects <18 years of age. Local IECs/IRBs will determine the age at which assent must be obtained from the subject.

090177e1811d3ccb\Approved\Approved On: 19-Feb-2010 20:59

The informed consent and assent form used in this study, and any changes made during the course of the study, must be prospectively approved by both the IRB/IEC and Pfizer before use.

The investigator must ensure that each study subject, or his/her legally acceptable representative, is fully informed about the nature and objectives of the study and possible risks associated with participation. The investigator, or a person designated by the investigator, will obtain written informed consent from each subject or the subject's legally acceptable representative before any study-specific activity is performed. The investigator will retain the original of each subject's signed consent form.

12.4. Reporting of Safety Issues and Serious Breaches of the Protocol or ICH GCP

In the event of any prohibition or restriction imposed (ie, clinical hold) by an applicable Competent Authority in any area of the World, or if the investigator is aware of any new information which might influence the evaluation of the benefits and risks of the investigational product, Pfizer should be informed immediately.

In addition, the investigator will inform Pfizer immediately of any urgent safety measures taken by the investigator to protect the study subjects against any immediate hazard, and of any serious breaches of this protocol or of ICH GCP that the investigator becomes aware of.

